Adverse events reporting will include the categories of cardiac, respiratory, vascular, bleeding, neurological (stroke/TIA), other organ complications and infection. Adverse events will be monitored by research staff and the investigator from the time of cardiac surgery until 365 days post procedure. AEs will be categorized according to seriousness and device and/or procedure relatedness. The monitoring of adverse events will occur from the time of cardiac surgery, throughout the hospitalization, at the 30 day, 6 week +/- 7 days, 6 months +/- 7 days and 12 months +/- 7 days post procedure assessments.

Serious adverse events or serious adverse device-related events will be reported to the FDA and Spectrum Health IRB per the regulations and reporting procedures.

If any thromboembolic events are observed during the study, an adverse event form will be submitted to the FDA. This report will include anonymized information on the procedure, type, and severity of thromboembolic event, the patient specific anticoagulation protocol, and the total number of subjects enrolled and treated in each arm by the event time.

Adverse events will be reported and recorded in REDCap and will include the following information:

- Date of onset first observation
- Description of event
- Seriousness of event
- Causal relationship to device/procedure
- Treatment required
- Outcome/resolution

The investigator and the non-study cardiothoracic surgeon will review all AEs.

For the purposes of this study certain events will be considered part of the expected post-operative course and will not be reported unless the investigator feels they deviate from the norm:

- Post-operative pain requiring medication
- Temporary mental status changes (except TIA/stroke)
- Mild GI disturbances, i.e. decreased appetite, nausea, vomiting, constipation or diarrhea
- Respiratory findings post-surgery, including oxygen usage, pleural effusion, atelectasis
- Minor laboratory findings, including hypokalemia, hyperkalemia, hypocalcemia, hypomagnesemia, leukocytosis, thrombocytopenia, hyperglycemia
- Post-operative anemia d/t intraoperative blood loss/dilution requiring ≤ 2 U transfusion
- Low-grade fever < 38.5∘ C
- Hypo/hypertension requiring treatment
- Mild creatinine increase, ≤ 0.3 mg/dL

Provisions to Monitor the Data for the Safety of Subjects

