Data will be reviewed by a non-study cardiothoracic surgeon; [name]. The review will include subject eligibility, documentation of the consent process, adverse events, and subject withdrawals. Review will occur after every 5 patients have a completed surgical procedure and are discharged from the hospital. Adverse Events (AE) will be evaluated for seriousness, unanticipated, procedural and/or device-relatedness. If any Serious Adverse Events (SAE) occur beyond what is expected in this patient population and are thought to be related to the limited left sided surgical maze procedure, the FDA and Spectrum Health IRB will be notified per reporting practices and the study may be terminated.

Monitoring of patient data will continue throughout the study at the scheduled assessment times.

Withdrawal of subjects

We do not foresee any circumstances in which subjects would want to withdraw from the study. However, subjects may withdraw from this study at any point, it will not be held against them nor involve penalty or loss of benefits to which subjects are otherwise entitled.

Risks/Benefits to Subjects

Neither LAA amputation or pulmonary vein isolation ablation, the 2 components of the limited left sided surgical maze procedure, have been shown to pose additional risk to the subject over the primary open heart procedure (7,8,16,28).

Potential adverse events with this combined procedure are similar to the risks of cardiac surgery and are listed below as described in the AtriCure® Synergy Ablation System Instructions for Use:

- Death
- Excessive bleeding that may require re-intervention
- Cardiac tamponade
- Pulmonary vein stenosis
- Restrictive or constrictive pericarditis
- Infection that may result in sepsis or endocarditis
- Myocardial infarction (MI)
- Stroke or transient ischemic attack (TIA)
- Thromboembolism
- Diaphragmatic (phrenic nerve) paralysis
- Esophageal-left atrial fistula or esophageal rupture
- Atrial perforation or rupture
- Ventricular perforation or rupture
- Atelectasis
- Pneumonia
- Congestive heart failure
- Cardiac valve injury
- Persistent pneumothorax
- Excessive pain and discomfort
- Deep sternal wound infection (mediastinitis)
- Perioperative atrial or ventricular rhythm/conduction disturbance
- Pericardial effusion
- Injury to the great vessels
- Injury to unintended surrounding tissues, including tears and punctures
- Extension of cardiopulmonary bypass time or aortic cross clamp time

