There are subsets of cardiac surgical patients where a prophylactic maze has already shown benefits because the risk of developing POAF is so high and the adverse sequela so morbid. It is recommended that a prophylactic maze be considered in the setting of re-operative open heart surgery patients with a dilated right or left atrium (19). A prophylactic maze is also warranted in the subset of patients who undergo a combined mitral valve and tricuspid valve operation even if they are in sinus rhythm (14).

If our hypothesis proves true, the benefits of a prophylactic limited left sided surgical maze procedure will impact thousands of cardiac surgical patients. At a minimum, those over age 70 have a 30% chance of developing POAF with any open heart surgical procedure (11,12,15,18). The detrimental effects of this complication include stroke, hemodynamic instability, additional medications for rate control and anticoagulation with their side effects, and prolonged length of hospital stay. Even if patients revert back to sinus rhythm they are discharged on additional medications to prevent recurrence and stroke. Anticoagulation alone for POAF carries a 3-4% annual risk of major hemorrhage (32). The 20% of patients who remain in POAF have a lifelong risk of increased stroke and decreased survival (9,20,22). Such risks are by far more serious than any risk posed by a prophylactic limited left sided surgical maze procedure which carries a risk of less than 1% for any complication. Thus should our strategy successfully reduce or eliminate the incidence of POAF, the immediate benefit to cardiac surgical patients will be immense and markedly decrease the burden on the health care system.

Provisions to Protect the Privacy Interests of Subjects

Explanation of the study and consenting will be done in a private area of Spectrum Health. HIPPA will be followed according to standard practice.

Confidentiality of Data

Only IRB approved research staff will have access to study data. Subject binders will be kept in a secure area of the CV Research office. REDCap will be utilized, the database is password protected. Data will be stored according to current policy and procedure.

Medical care and compensation for Injury

While not anticipated, if subjects are injured or made sick from taking part in this research, medical care will be provided. No funds have been set aside to pay subjects in the unlikely event of a research related injury.

Cost to Subjects

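### The rule on notification and possible termination depends on attributing events to the maze, with no safety counts by arm, so an excess of common serious events in the maze arm may not trigger it

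*Combined protocol and SAP*

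**What the plan says.** All of this is in the combined protocol and SAP.

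- **Provisions to Monitor the Data for the Safety of Subjects.** One non-study cardiothoracic surgeon reviews eligibility, consent, adverse events and withdrawals. On timing: "Review will occur after every 5 patients have a completed surgical procedure and are discharged from the hospital". Each adverse event is classified for seriousness, for being unanticipated, and for relation to procedure or device. If SAEs "occur beyond what is expected in this patient population and are thought to be related to the limited left sided surgical maze procedure", then "the FDA and Spectrum Health IRB will be notified per reporting practices and the study may be terminated". This is the only sentence in the protocol on stopping the study. It gives no expected rate, no source for one and no comparison between arms.
- **Adverse events.** The general reporting rule is: "Serious adverse events or serious adverse device-related events will be reported to the FDA and Spectrum Health IRB per the regulations and reporting procedures". The investigator and the non-study surgeon review all adverse events. A separate rule reads: "If any thromboembolic events are observed during the study, an adverse event form will be submitted to the FDA". That report includes "the total number of subjects enrolled and treated in each arm by the event time".
- **Risks/Benefits to Subjects.** "Potential adverse events with this combined procedure are similar to the risks of cardiac surgery"; the list that follows includes death, bleeding, tamponade, infarction and stroke. The section says neither component of the maze has been shown to add risk to the primary operation. It later contrasts the harms of postoperative atrial fibrillation with "a prophylactic limited left sided surgical maze procedure which carries a risk of less than 1% for any complication". A shorter list of risks that may be associated with the maze includes bleeding, need for a permanent pacemaker and atrial flutter.
- **Safety endpoints.** The 30-day components include all-cause death, TIA or stroke, procedure-related bleeding and permanent pacemaker. No link to the monitoring rule is stated.

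**The concern.** The two conditions are joined by a conjunction, and the second is a causal judgement on events that also occur in ordinary cardiac surgery. A reviewer looking at one stroke or one reoperation has little in the case itself to separate a maze effect from background surgical risk, and the protocol's stated expectation is that the maze adds none. The randomised control arm is the evidence that can separate the two, but the monitoring section does not call for it.

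At stake is the decision whether to continue. Patients without a history of atrial fibrillation receive an added procedure. An excess of common serious events among them could build up across reviews without anyone being required to set the two arms side by side.

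**Working it through.** The rule contains no rate, limit or error probability, and Sample Size Determination fixes 60 patients without a calculation. There is no figure of the plan's to reproduce, so the check is mainly of the wording, with arithmetic for illustration.

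**1. The trigger.** Condition A is that SAEs exceed expectation in this population. Condition B is that they are thought related to the maze. Both must hold. Condition A is undefined: it can mean an unusual type of event or an unusual frequency. On the frequency reading, an excess of common events could satisfy A, but B must still be met. B is judged against a risk section that calls the maze's risks similar to those of the operation and not additional. B can therefore fail when A holds.

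**2. What still gets through.**

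| Route | Relatedness needed? | Counts by arm? |
|---|---|---|
| Non-study surgeon reviews all adverse events | No | Not specified |
| SAEs to FDA and IRB, per regulations | None stated | Not specified |
| Thromboembolic events to FDA | No | Numbers enrolled and treated per arm; cumulative events by arm not listed |
| Notification with possible termination | Yes, and beyond expectation | Not specified |

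Individual events are visible by several routes. A cumulative comparison by arm is specified in none of them.

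**3. Illustration of size (event rates assumed; 30 per arm from Sample Size Determination).** Expected patients with an event = rate × 30.

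| Control vs maze rate | Expected patients | Background among maze events |
|---|---|---|
| 5% vs 15% | 1.5 vs 4.5 | 1.5 |
| 10% vs 20% | 3 vs 6 | 3 |
| 10% vs 30% | 3 vs 9 | 3 |

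In the last row 9 − 3 = 6 events are excess, but nothing in a single case marks it as one of the 6. The split is visible only by arm.

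**4. Would a significance test be enough?** No. For 9 of 30 against 3 of 30, the two-sided Fisher exact p-value is 0.104, just above the 0.10 level in Statistical Methods (which does not state sidedness; two-sided is assumed here). The chance of a significant excess in the maze arm with that test is 17% at 5% vs 15%, 16% at 10% vs 20%, and 49% at 10% vs 30%. The reviewer needs the raw counts.

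**5. Would an automatic trigger on any excess be sensible?** No. There would be 60 / 5 = 12 reviews. Simulating 30 patients per arm with equal event rates in both arms, the cumulative maze count exceeds the control count at one or more reviews in about 55%, 66% and 74% of trials at assumed rates of 5%, 10% and 20%.

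**6. The two reporting passages.** The monitoring sentence says what happens if both conditions hold; it does not say only if. Both passages defer to regulations or reporting practices, so both can be followed. Their scope differs on its face, however: SAEs in general in one, only unexpected and maze-related SAEs in the other. If the first means all SAEs, the notification clause in the second is redundant.

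**The case against.** The strongest reply is that little is hidden. All adverse events go to the non-study surgeon, SAEs go to the FDA and IRB, and thromboembolic events, which would cover embolic stroke, go to the FDA regardless of cause with per-arm denominators. The trial is unblinded and reviews are frequent, so nothing prevents the reviewer from counting by arm. The claim of less than 1% risk can even sharpen suspicion: at exactly 1%, the probability of 3 or more maze complications in 30 patients is 0.3% (binomial), so a cluster recognised as such would stand out.

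Most of this stands, and it rules out two stronger readings that a reader might infer. One is that the rule can never be met, however large the imbalance. The documents do not support this: expectation may be read as frequency, and bleeding and pacemaker need are named as possibly maze-associated. The other is that the two passages contradict each other on SAE reporting. They do not; they overlap and leave the threshold unclear. Nor do the documents support the view that events would be withheld from the reviewer, IRB or FDA.

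The reply does not close the gap. Being able to count by arm is not the same as being asked to, and the 1% argument helps only once events have been recognised as maze complications, which is the step in doubt.

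**Conclusion.** The point holds in a limited form. An excess in the maze arm of serious events common to cardiac surgery may fail the relatedness condition and so may not trigger the rule, because review is event by event and no counts by arm are specified. The gap lies in the decision whether to continue, not in the reporting of individual events.

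This rests on the text. The size cannot be derived from the documents: the 3 against 9 illustration, the test properties and the simulation all depend on assumed event rates. For an unblinded 60-patient feasibility study, the change is worth making because it is cheap and concerns safety.

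**What to change.** In Provisions to Monitor the Data for the Safety of Subjects:

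1. At each scheduled review, give the non-study surgeon cumulative counts, by arm and regardless of attributed cause, of each safety-endpoint component and of all SAEs, with the number operated on in each arm.
2. State that the reviewer may refer a between-arm imbalance that causes concern to the IRB and FDA even if no single event is judged maze-related.
3. Do not make a numerical excess over concurrent controls an automatic trigger. Simply replacing the conjunction by an alternative, with controls as the expected rate, would set off false alarms in most harmless trials (step 5 of the working). Any pause or stop criterion is for the sponsor and reviewers to set.
4. State that the Adverse events section governs SAE reporting, and that the monitoring sentence concerns the decision whether to continue.

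The cost is a few sentences and a short table from data already collected in REDCap. No masking is lost. The small downside is that chance imbalances in small numbers will be seen and discussed.

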Prophylactic Limited Left Sided Maze Procedure to Prevent Post-Operative Atrial Fibrillation in Adult Cardiac Surgery Patients

(PREVENT AF-Feasibility Study)

Investigator: [name], FACS

CV Cardiothoracic Surgery

Spectrum Health [name]

Version Date: February 17, 2020

Objective

To evaluate the safety and effectiveness of a prophylactic limited left sided maze procedure in subjects undergoing cardiac surgery to decrease the incidence of post-operative atrial fibrillation (POAF).

Background

Atrial fibrillation (AF) is the most common complication following adult open heart surgery and is the leading cause for prolonged hospital stay (1,2). The incidence of this common post-operative complication is 30 to 60% (1,25). POAF places enormous strain on hospital resources and subjects' immediate post-operative wellbeing. More importantly, patients who experience POAF have decreased long-term survival (33,34). Currently there is no effective treatment to prevent POAF (25,26). Although multiple preventative therapies have been trialed the overall incidence remains at around 40% (Society of Thoracic Surgeons Database 2017). New treatment strategies are needed to reduce or eliminate the occurrence of POAF. An effective strategy would lessen the associated morbidities such as hypotension and heart failure, exclude the additional medications especially anticoagulants, and negate the added hospital length of stay (LOS) incurred by this complication.

AF is an abnormal and irregular heart rhythm in which electrical signals are generated chaotically throughout the upper chambers (atria) of the heart. Studies have demonstrated increased risk factors for the development of POAF (11,12,15). The predominant risk factor is age. Age 70 or greater predicts a minimum 30% risk of POAF with isolated coronary artery bypass grafting (CABG) surgery (11,12,15,18). An isolated aortic valve replacement (AVR) in this age group carries a 40% risk while a combined AVR/CABG, MVR (mitral valve replacement)/CABG or AVR/MVR have a 60% risk of POAF (18,25). Although there are other published risk factors which increase the occurrence of POAF such as low ejection fraction, peripheral arterial disease, diabetes, chronic obstructive pulmonary disease, or renal failure; they are not consistent throughout the literature (11,12,15,18).

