European Society of Cardiology conclusively demonstrated that surgical occlusion of the LAA markedly decreased the risk of stroke in comparison to controls: at 3.7 years 6% in patients with no LAA versus 18% in the control population(42).

[figure not shown]

Figure 2. Pulmonary vein isolation procedure

Hypothesis

We hypothesize that performing a prophylactic limited left sided surgical maze, i.e., pulmonary vein isolation and excision of the left atrial appendage, in a group of at risk cardiac surgical patients at the time of the index procedure, will reduce the incidence of POAF. The null hypothesis is that the prophylactic surgical ablation will have no effect on the incidence of POAF.

Setting of the Research

This study will be conducted at a single center, Spectrum Health. The PI and all Spectrum Health cardiothoracic surgeons participating in the study are highly qualified and certified by the American Board of Thoracic Surgery. They are all proficient in performing the maze procedure as it is commonly utilized in everyday practice to manage and treat AF.

Subjects will be seen in the cardiothoracic surgeon's office and/or the hospital inpatient setting. The surgery will be performed at the Meijer Heart Center, Spectrum Health Hospitals.

Resources Available to Conduct this Research

Spectrum Health cardiothoracic surgeons perform approximately 1200 heart surgeries per year. Approximately 300 of these surgeries which include isolated coronary artery bypass grafting (CABG), isolated aortic valve replacement (AVR), or combined AVR/CABG are performed in patients ≥ 70 years of age. Therefore, we do not anticipate difficulty recruiting the necessary number of subjects during the enrollment period.

The PI will have dedicated research time in his schedule. Experienced research staff from the CV Structural Heart Team will assist with the study as delegated by the PI.

Study Design

This is a single-center, prospective, randomized, unblinded, interventional feasibility study to determine whether or not a prophylactic limited left sided surgical maze procedure is effective in reducing or preventing POAF. A high risk population with no history of atrial fibrillation or flutter, with a baseline risk of POAF of 40% or greater will be chosen. This includes CABG/AVR, isolated AVR, and isolated CABG patients 70 years and older. Up to 60 subjects who are scheduled to undergo elective open heart surgery will be randomized 1:1 into one of two study arms:

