- 1. Control arm: Elective open heart surgery without a limited left sided maze procedure.
- 2. Treatment arm: Elective open heart surgery with a limited left-sided maze procedure.

Sample Size Determination

No sample size calculation was performed as this is a feasibility trial and the number is fixed at 60 patients where 30 will be randomly assigned to the control arm and 30 randomly assigned to the treatment arm.

Statistical Methods

Summary statistics will be calculated. Quantitative variables will be expressed as mean ± standard deviation or median [interquartile range]. Qualitative variables will be expressed as frequency (percent). To determine if there is an association in POAF and the two arms of the study, a Chi-Square Test or Fishers Exact test will be used depending on assumptions being met. To look at our secondary outcomes such as hospital length of stay and incidence of postoperative reoperations for bleeding, a two sample t-test or Wilcoxon Rank Sum will be used to determine if there is a difference between the two groups and those that had POAF vs. those that didn't. Significance will be assessed at the 0.10 level. A level of 0.10 will provide more power to the study while only allowing a slight increase in error.

Recruitment methods

All subjects who receive an inpatient or outpatient heart surgery consult and meet the criteria may be approached about study participation. Consults will occur in the Cardiothoracic Surgeon's office of the Meijer Heart Center or Spectrum Health inpatient units. The subject's electronic medical records (EMR), Cerner and Epic, will be reviewed. There are no plans for advertisement or patient payment related to study participation.

It is expected enrollment will take approximately 6 months.

Inclusion and Exclusion criteria

Inclusion Criteria

- 1. Male or female
- 2. Age \geq 70 years
- 3. Elective cardiac surgery: isolated AVR, isolated CABG, or AVR/CABG,

Exclusion Criteria

- 1. A history of AF or atrial flutter
- 2. Less common cardiac operations such as aortic root replacements, aortic dissections, myxoma excisions, or pericardectomies. Beating heart or off-pump procedures, redo open heart procedures.
- 3. Subjects with existing pacemaker and/or AICD
- 4. Vulnerable populations; adults unable to sign consent, prisoners
- 5. Need for emergent or salvage surgery for any reason
- 6. Currently participating in an investigational drug or another device study (excluding registries)

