- 7. Subjects currently on antiarrhythmic drugs Class I and III including amiodarone.

Study endpoints

The incidence or absence of documented AF, defined by Society of Thoracic Surgeons (STS) registry data as the occurrence of POAF or atrial flutter that requires treatment, is the primary endpoint (21). In addition, length of stay (LOS) and additional antiarrhythmic or anticoagulant medications will be examined as a secondary endpoint.

Safety endpoints

The safety endpoint is the occurrence of one of the following events between time of procedure and the 30 day post procedure assessment:

- All-cause death
- TIA/stroke
- Bleeding (chest tube drainage) that is procedure related and requires take back to the operating room or blood transfusions
- Incidence of AF
- Need for permanent pacemaker
- Evidence of pulmonary vein stenosis defined as > 50 % occlusion of the vessel.

Procedures Involved in the Research

Baseline preoperative cardiac surgery workup will be done on all patients according to standard of care. This workup will consist of:

- History and physical exam
- Chest X-Ray

- Electrocardiogram
- Echocardiogram
- Cardiac catheterization
- Blood and urine tests such as complete blood count, complete metabolic count, cardiac enzymes, type and screen, and urinalysis. Any other indicated tests based on patient history and index procedure i.e.; pulmonary function tests, carotid ultrasound, leg vein mapping, noncontrast chest CT.

Prior to enrollment, the protocol and informed consent must be approved by the Spectrum Health Institutional Review Board (IRB). IRB approved Health Insurance Portability and Accountability Act (HIPPA) will also be used. A regulatory binder and subject binders will be created according to local requirements and stored in the CV Research Department.

Before the subject signs the informed consent form (ICF), the investigator or designated study personnel will explain the research, study procedure, anticipated benefits, and potential risks of study participation. Adequate time will be allowed to read the ICF and ask questions. The original signed ICF will be kept with the subject's research records and a copy will be given to the subject.

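### Safety is an objective, but no safety outcome gets a confidence interval; with 30 patients per arm, neither p>0.10 nor a zero count for a rare complication is evidence of safety.

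*Combined protocol and SAP*

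**What the plan says.** The Objective is "To evaluate the safety and effectiveness of a prophylactic limited left sided maze procedure in subjects undergoing cardiac surgery". Under Safety endpoints, "The safety endpoint is the occurrence of one of the following events", counted from the procedure to the 30-day assessment. The six events are death from any cause, TIA or stroke, procedure-related bleeding needing reoperation or transfusion, AF, permanent pacemaker, and pulmonary vein stenosis.

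Sample Size Determination states: "No sample size calculation was performed as this is a feasibility trial and the number is fixed at 60 patients", of whom "30 will be randomly assigned to the control arm and 30 randomly assigned to the treatment arm".

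Statistical Methods never mention the safety endpoint by name. What could apply to it is this:
- Qualitative variables are summarised as a count and percentage.
- For POAF, "a Chi-Square Test or Fishers Exact test will be used depending on assumptions being met".
- Reoperation for bleeding is listed with length of stay as a secondary outcome, to be compared by a two-sample t-test or Wilcoxon rank-sum test.
- "Significance will be assessed at the 0.10 level".

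No confidence interval, margin or acceptable event rate is given for any safety outcome.

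The section on monitoring the safety of subjects provides for review by a non-study surgeon after every 5 discharged patients. The study may be terminated for maze-related serious events beyond expectation, but no expected rate is stated.

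Risks/Benefits to Subjects speaks of a "prophylactic limited left sided surgical maze procedure which carries a risk of less than 1% for any complication", with no citation, denominator or time window. The same section says that atrial flutter after isolated pulmonary vein isolation has not been quantified.

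**The concern.** The maze is added in patients with no history of AF, so any harm it adds is half of the question the trial asks. The analysis tools in the plan suit a common outcome such as POAF. Applied to rare complications, they will usually produce a small count and a p-value above 0.10, whether or not the procedure adds several points of risk. Without an interval, nothing in the results shows how little such a finding excludes. A reader who has already met the protocol's statements that the procedure adds no risk could take the result as support for them.

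Two features add to this. Reoperation for bleeding, a yes/no event, is assigned tests meant for quantitative data. And the composite safety endpoint contains AF, which the maze is meant to reduce, so benefit and harm are summed in one number.

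**Working it through.** **Inputs from the documents.** n = 30 per arm (Sample Size Determination); alpha = 0.10 (Statistical Methods; sidedness not stated, two-sided assumed); baseline POAF risk 40% or greater (Study Design). The documents give no expected rate for any other safety component, so the complication rates below are assumptions, shown as a range. I also assume no dropout and that all patients are treated as assigned.

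**The plan's own figure.** The figure of less than 1% cannot be reproduced, because no events or denominator accompany it. There is no sample size calculation to reproduce either.

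**1. What a zero or single count excludes.** For 0/30 the exact (Clopper-Pearson) upper limit is 1 − a^(1/30).
- One-sided 95%: 1 − 0.05^(1/30) = 9.5%.
- Two-sided 95%: 1 − 0.025^(1/30) = 11.6%.
- For 1/30 the two-sided upper limit is 17.2%.
- With 0/30 in both arms, the 95% Newcombe interval for the risk difference is −11.4 to +11.4 points.
- Zero-event sample needed to exclude 1%: ln(0.05)/ln(0.99), rounded up, is 299 maze patients (one-sided), or 368 with 0.025 (two-sided). That is about 10 to 12 times the planned 30.

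**2. How often a zero count occurs.** P(0/30) = (1 − p)^30.

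| True risk | P(0/30) |
|---|---|
| 0.5% | 86% |
| 1% | 74% |
| 2% | 55% |
| 5% | 21% |
| 10% | 4% |

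A zero count is likely near 1% and still occurs about one time in five at 5%.

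**3. What the 0.10 test can detect.** With sparse counts the chi-square assumptions fail, so Fisher's test applies. With no control events, the two-sided p for t maze events is 2 × C(30,t)/C(60,t): 0.237 for t = 3, 0.112 for t = 4 and 0.052 for t = 5. So five maze events (17%) are needed against none; against one control event, seven are needed. Exact power by full enumeration:

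| Control v maze (assumed) | Power |
|---|---|
| 2% v 4% | 0.4% |
| 2% v 6% | 1.8% |
| 5% v 10% | 5% |
| 3% v 10% | 8% |
| 3% v 13% | 18% |
| 2% v 20% | 56% |

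The test's real size is 0.7% when both arms have 5% events and 2.6% at 10%, not 10%. For 80% power, 5% v 10% would need 343 patients per arm.

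**4. The t-test or Wilcoxon on a yes/no event.** Take reoperation for bleeding at 3/30 v 0/30. The t-test gives p = 0.078 and the Wilcoxon test (normal approximation, no continuity correction) gives 0.078. Fisher's test gives 0.237. The named tests would call this significant at 0.10 and the exact test would not, so the choice of test alone decides the result.

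**5. The composite.** With AF at 40%, P(0/30) = 0.6^30, about 2 in 10 million; even at 20% it is 0.1%. If AF dominates, Fisher's power is 42% for 40% v 20% and 80% for 40% v 10%. An invented illustration of masking: AF falls from 12/30 (40%) to 6/30 (20%), while 3 maze patients without AF and no control patients have a stroke or need a pacemaker. The composite is then 12/30 in control against 6 + 3 = 9/30 with maze. It favours the maze although the other harms are 3 v 0.

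**The case against.** The strongest reply is that this is a declared feasibility study with a fixed number of patients. Low power for rare harms comes with that design and is not hidden. That stands, and nothing here asks for more patients. But small size is a reason to plan intervals, because they make the limitation visible; it does not justify a significance threshold for safety.

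Second, safety oversight exists: review after every 5 discharges, adverse event follow-up to 365 days, and reporting of thromboembolic events to the FDA with the numbers treated per arm. This also stands. The plan lacks a numerical limit, not all safeguards. These provisions govern conduct, however, and do not say how the final safety data are to be analysed or read.

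Third, a reader might infer that a zero count or a non-significant result is close to guaranteed. The documents do not support that in general. A zero count falls to 21% probability at a true risk of 5%. Power reaches about 56% for 2% v 20%. For the composite as defined, with AF inside it, zero is practically impossible and a significant difference is quite possible.

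Fourth, a reader might infer that the trial sets out to confirm a risk below 1%. It does not say so. That figure appears once, as justification in the risk/benefit discussion, and the only null hypothesis concerns POAF. Reading the results as confirmation is a foreseeable mistake that the plan does not guard against; it is not a stated aim.

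**Conclusion.** The concern holds for rare individual complications and for how the composite is read. The plan gives no interval for any safety outcome. For components such as death, stroke, pacemaker or pulmonary vein stenosis, 30 v 30 gives about 5% power or less against an excess of up to about 5 points, and 0/30 leaves a two-sided 95% upper limit of 11.6%. Neither p>0.10 nor a zero count would therefore be evidence of safety, and the data cannot support a risk below 1%. Separately, AF inside the composite could mask an excess of the other events, and the test named for reoperation for bleeding does not suit a yes/no outcome.

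The interval limits depend only on n = 30. The power figures rest on assumed event rates and a two-sided test. This should be changed before analysis; it does not call the design itself into question.

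**What to change.** In Statistical Methods, add the following:

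- Report each safety component by arm as n/N with an exact 95% interval, and the risk difference between arms with its 95% interval.
- Report the 30-day composite twice, with and without AF.
- Do not judge safety by the 0.10 test, and do not apply a t-test or Wilcoxon test to yes/no events, including reoperation for bleeding.
- State that p>0.10 or 0/30 does not show safety, that 0/30 remains compatible with a risk of up to 11.6%, and that the trial cannot confirm the figure of less than 1%.

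The cost is a paragraph of wording and one more table. No extra patients, visits or data are needed, since the components are already due to be collected. The downside is a less favourable safety statement.
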